
The COVID-19 pandemic has required many organisations to implement telehealth as a way of delivering care. Many services which were previously only provided face to face, or through outpatients, have now been successfully transitioned to a telehealth service. There are still issues with telehealth delivery, including device and internet capabilities at the consumer end, the unfamiliarity of the user interface, and uncertainty regarding the cost effectiveness at the provider end.

Although intensive interventions including multidisciplinary care, and home visits have been shown to reduce short term readmissions, they may not be cost effective in all settings, and are difficult to implement across an organisation. Low intensity interventions such as phone calls are easy to implement, however, have not been shown by themselves to impact on readmission rates⁽¹⁵⁾. What is needed is a low-cost intervention which combines multiple interventions into a coordinated package, which can be delivered without requiring face to face or outpatient consultations, and which if successful, can be readily spread across an organization.

A recent feasibility study (Telehealth Transition of Multimorbid Individuals [TTOMMI] study) conducted at the Royal Adelaide Hospital demonstrated acceptability, feasibility, and usefulness of a transition care coordination service for both patients and staff. Moving forward, the aim of this pragmatic randomised control study is to develop and test a transitional model of care to optimally support people living with multimorbidity, via telehealth, and decrease hospital readmissions. The study is expected to commence 1 July 2023, and complete 1 February 2025.

STUDY PURPOSE

The main purpose of this study is to implement a transitional model of care to minimise unnecessary hospital admissions and emergency department presentations for patients with multimorbidity. The research study is being implemented initially at the Queen Elizabeth, and then the Royal Adelaide Hospitals. This is because the Central Adelaide Local Health Network (CALHN) does not have embedded transition care coordination pathways, protocols, or services. This is significant because transition coordination between the primary and secondary healthcare sectors has been shown to decrease hospital readmissions and increase primary healthcare use.⁽¹⁶⁾

AIM AND HYPOTHESIS

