
• Inpatients (ward or emergency department)• Sufficient cognitive function and English language skills to provide informed consent and complete assessments. (Although interpreters are readily available in the inpatient setting, the main components of this intervention are via telehealth in the transition period after discharge Therefore although we will be able to communicate with the participant's family regarding their care and needs whilst in hospital, interpreter services may not be available via telehealth post-discharge. Also, given that the informed consent form and some written assessments are in English, they need to have adequate English language skills to provide written informed consent).• Ability to engage in telehealth• A history of either diabetes with cardiovascular disease, or comorbidity in at least 3 of the following illness domains:
○ Diabetes: type 1 or type 2○ Cardiovascular disease: symptomatic atherosclerotic disease (ischemic heart disease, cerebrovascular disease, peripheral vascular disease, symptomatic valvular heart disease or atrial fibrillation○ Chronic cardiac failure○ Psychiatric illness including mood or anxiety disorders○ Respiratory disease including chronic obstructive airways disease, asthma, or interstitial lung disease○ Kidney disease resulting in chronic renal impairment with creatinine clearance ≤ 30 ml/min○ Current active malignancy.	
• Patients living in or likely to be discharged to high level residential aged care facility• Patients enrolled in a comprehensive management program on discharge, e.g., formal rehabilitation program, rehabilitation in the home, heart failure outreach service, COPD pulmonary rehabilitation, hospital in the home, or receiving disability or community psychiatric services including care coordination• Patients followed up through other local health network (LHN) services providing community outreach such as patients who are homeless• Patients with a current history of illicit drug or alcohol dependence which may interfere with ability to engage with the program• Patients with palliative intent and likely to have a life expectancy of less than 6 months• Patients due for elective readmission within 2 weeks of current hospital discharge• Insufficient cognitive function or English language skills to provide informed consent and complete assessments.

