Following discharge, the TC will provide transition coordination via telehealth for up to 6 weeks, as indicated by patients' clinical stability. The TC will contact the patient post-discharge at 48 hours, then 1 week later, then 4 weeks later. Clinical assessment by the TC may indicate more frequent phone calls monitoring or intervention are required. During telehealth calls, the TC will review: the TAP, symptoms, appointments attended, medication management, and domestic and health services required/accessed. The TC will undertake appropriate actions (e.g., service referral or follow-up, patient education, liaison with healthcare providers) to coordinate the transition of the patient back to primary care. This will particularly involve liaison with the general practitioner team including the practice nurse involved in the patient's chronic disease care planning. A multidisciplinary case discussion will be held approximately 4- 6 weeks post-discharge between the TC and clinical team.

Handover

The TC holds a final telephone consultation with the patient at 6-10 weeks post-hospital discharge, completes a final assessment, and discharges the patient from the transitional care service. The TC then provides the patient's GP with a letter summarising the issues identified, actions taken, and recommendations for ongoing care.

Outcomes

Primary

- Rate of representation to hospital (emergency department or hospital admission) within 3 months of discharge from index admission

Secondary outcomes

Health care utilisation

- Rate of representation to hospital (emergency department or hospital admission) within 1, 6 and 12 months of discharge from index admission
- Overall length of hospital stay within 1, 3, 6 and 12 months of discharge from index admission
- Cost of transition service model of care

Patient outcomes

- Patient-reported symptom burden
- Patient symptom management/self-efficacy
- Quality of life

- Patient experience, satisfaction, and perceived continuity of care

Organisation of care

- Implementation of components of transitional care model
- Implementation of transition action plan for all patients

Data collection

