The main aim of a sample size calculation will be to determine the number of participants needed to detect a clinically relevant effect of the transitions service intervention. (Charan and Biswas 2013) . As discussed above the patient population has been selected to have a high baseline readmission rate, and these patients are known to have a high proportion of preventable readmissions attributed to poor care coordination. Our previous data has demonstrated that a similar group of patients (those with diabetes and cardiovascular disease (HREC/18/CALHN/120)) have a 25-30% representation rate within 28 days of discharge. As this intervention is anticipated to be up to 6 weeks, and the effect is expected to help prevent representations beyond this time, our primary endpoint will be to evaluate representation to the emergency department or readmission within 3 months.

Our previous study demonstrated that approximately 40% of patients had a representation by 3 months. The readmission rate in this study may be higher due to enrolment of patients with greater multimorbidity, and the exclusion of patients already receiving other CALHN services.

We anticipate that the enrolment of approximately 200 patients over 18 months will be feasible and provide us with sufficient sample size to achieve the primary outcome with the likely baseline readmission rate in the control group and absolute reduction in the intervention group (Table 4). Given that the primary endpoint will be derived from SA health information systems, and the study has an intention-to-treat approach, there will be need to consider a larger sample size for consideration of withdrawals, drop-outs, or loss to follow up.

Table 4. Sample size per group by baseline readmission rate and absolute reduction in readmission with 80% power and $\alpha=0.05$

Absolute reduction in readmission rate in intervention group	Baseline readmission rate in control group at 3 months		
	35%	40%	45%
15%	136	150	160
20%	70	79	86
25%	40	47	52

Statistical methods to be undertaken

An intent-to-treat approach will be used. Linear regression analyses will be conducted to estimate effects of the intervention on primary and secondary outcomes. A hospital fixed effects model will be used to account for stratification at the hospital level. Sensitivity analyses will be performed to assess the robustness of the findings.

DATA SECURITY AND HANDLING

Data management and storage

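### The primary outcome counts planned admissions in weeks 3 to 13 as events, although the service is meant to prevent unnecessary ones

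*Protocol*

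**What the plan says.** The Outcomes section of the protocol defines the primary as "Rate of representation to hospital (emergency department or hospital admission) within 3 months of discharge from index admission". The section on sample size repeats it, equally unqualified: "our primary endpoint will be to evaluate representation to the emergency department or readmission within 3 months". Neither place separates emergency from elective admissions. (The Synopsis gives 1 month for its primary objective. That conflict is a separate matter, and this point uses the 3-month definition, on which the sample size rests.)

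Planned admissions are addressed only through eligibility. The Synopsis and Table 1 both exclude "Patients due for elective readmission within 2 weeks of current hospital discharge".

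The Study Purpose section says the service is there to "minimise unnecessary hospital admissions and emergency department presentations for patients with multimorbidity". The sample size section supports the expected effect by stating that "these patients are known to have a high proportion of preventable readmissions attributed to poor care coordination". The planning rate comes from the team's previous study, in which "approximately 40% of patients had a representation by 3 months". The protocol does not say how much of that 40% was elective.

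**The concern.** Three months is about 91 days and the eligibility rule reaches 14 of them. It also works only on what is already scheduled at enrolment. As the outcome is written, an elective admission from week 3 onward is a primary event, and so is one arranged after enrolment.

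A transition coordinator cannot be expected to prevent a scheduled admission. If such admissions occur equally in both arms, they add events that carry no treatment effect. The absolute difference shrinks and power falls. The design has limited room for this: at a 40% control rate, Table 4 asks for 79 per group for a 20-point reduction but 150 per group for 15 points, and about 100 per group are planned.

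**Working it through.** **Inputs from the protocol.** About 200 patients randomised 1:1, so 100 per arm; control risk 40% at 3 months; reductions of 15, 20 or 25 points; 80% power; alpha 0.05. Two-sided testing is not stated, but it reproduces the table. No single design effect is named. The 20-point reduction is used here because it is the smallest in Table 4 that 100 per arm covers at a 40% control rate.

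**Reproducing Table 4.** With unpooled variance and no continuity correction,

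n = (z₀.₉₇₅ + z₀.₈₀)² × [p₁(1−p₁) + p₂(1−p₂)] / (p₁−p₂)².

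For 40% versus 20%: (1.960 + 0.842)² × (0.24 + 0.16) / 0.04 = 78.5, rounded up to 79, as stated. The same formula gives all nine cells exactly, so the table's arithmetic is not in question.

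**Power at 100 per arm.** With the pooled variance under the null and p̄ = (p₁+p₂)/2,

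power = Φ{ [ |p₁−p₂|√n − z₀.₉₇₅ √(2p̄(1−p̄)) ] / √(p₁(1−p₁) + p₂(1−p₂)) }.

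For 40% versus 20%: (2.000 − 1.270) / 0.632 = 1.154, so power is 87.6%.

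**Adding planned admissions.** Let e be the 3-month probability of a planned admission. It is assumed equal in both arms and independent of unplanned events. The protocol gives no value, so 2%, 5% and 10% are shown.

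- *Case A: the 40% is unplanned only.* Unplanned risk is 40% versus 20%, and planned events come on top. All-cause risks are 1 − 0.6(1−e) and 1 − 0.8(1−e), so the difference is 0.20(1−e).
- *Case B: the 40% already includes planned events.* Unplanned control risk is u = 1 − 0.6/(1−e), and the service halves it. The all-cause risk on intervention is 1 − (1−u/2)(1−e), so the difference is (0.40−e)/2.

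| e | Case | All-cause risks | Difference (points) | Power, all-cause | n per arm for 80% (unpooled) | Power, unplanned only |
|---|---|---|---|---|---|---|
| 0 | both | 40.0% vs 20.0% | 20.0 | 87.6% | 79 | 87.6% |
| 2% | A | 41.2% vs 21.6% | 19.6 | 85.3% | 85 | 87.6% |
| 2% | B | 40.0% vs 21.0% | 19.0 | 83.6% | 89 | 86.1% |
| 5% | A | 43.0% vs 24.0% | 19.0 | 81.7% | 93 | 87.6% |
| 5% | B | 40.0% vs 22.5% | 17.5 | 76.5% | 107 | 83.5% |
| 10% | A | 46.0% vs 28.0% | 18.0 | 75.4% | 110 | 87.6% |
| 10% | B | 40.0% vs 25.0% | 15.0 | 62.1% | 150 | 78.1% |

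In case B at 10%, the diluted difference is the 15 points for which Table 4 already asks 150 per group.

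**The case against.** The best counter-argument is that all-cause counting may be intended. The Aim is broader than the Study Purpose: it speaks of less direct contact with hospitals in general. The hypothesis concerns short-term readmission without limiting it to unplanned events, and the trial is described as pragmatic with an endpoint taken from administrative records. This stands in part. The all-cause endpoint is not plainly an error, but the protocol gives no reason for choosing it, and the Study Purpose and the sample size rationale both point to avoidable admissions.

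A reader might take the 2-week exclusion as proof that planned readmissions were never meant to count. The protocol gives no reason for that rule, and it could equally serve to protect the early coordinator contacts. It shows a gap in coverage but does not establish intent.

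It can also be said that admission types are a detail for the SAP. An SAP may add such detail, but the protocol has already defined the outcome in two places without it, and narrowing that definition would change the endpoint.

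Finally, the planned rate is an assumption. At 2% the loss is only 2 to 4 points of power, and case A is milder than case B throughout. That is correct and limits how strongly the point can be put.

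**Conclusion.** The point holds as a mismatch between the primary outcome and what the service is said to prevent. Starting from 88% power, the loss is minor at a planned rate of 2% (power 84-85%). At 5% it matters (77-82%), and at 10% it is substantial (62-75%). These figures assume 100 per arm, a true effect that halves unplanned risk, and planned admissions that are equal by arm and independent of unplanned ones. If referrals by the coordinators changed planned admissions in one arm, the result would be bias and not only dilution. Nothing in the protocol allows its size or direction to be judged.

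Two stronger readings are not supported. A reader might infer that a death without representation is scored as a success and dilutes the effect. The protocol states no rule for deaths, and an SAP may supply one. With equal mortality before representation of 2% or 5% (assumed), power is 86.6% or 85.1%, a loss of about 1 to 3 points; unequal mortality would be a bias in either direction, not dilution. A reader might also see a fault in the exclusion of "Patients with palliative intent and likely to have a life expectancy of less than 6 months". Its 6-month horizon is twice the primary window, so it does not weaken the 3-month outcome.

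**What to change.** Define the primary outcome as at least one ED presentation or unplanned (emergency) admission within 3 months of index discharge. Use the admission-type field in the SA Health record, which is assumed to be available. Keep all-cause representation within 3 months as a secondary outcome. Check whether the 40% from the previous study included elective admissions, and restate the control rate for the chosen definition.

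If all-cause counting is deliberate, give the reason in the protocol and prespecify the unplanned-only analysis as a key sensitivity analysis.

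The cost is a change of wording and one more field in the data extract. There will be somewhat fewer events and a baseline rate to re-confirm. The change does not recover all the power if the 40% includes planned events: in case B the unplanned-only endpoint has 83.5% power at 5% and 78.1% at 10%, against 76.5% and 62.1% for all-cause.

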► *Will data be re-identifiable?*

All identifiers will be removed from the dataset by the TCs or [name], and re-identified with a replacement code, after patients are discharged from the Transition Care Service. (e.g., name, postcode, date of birth). Re-identification will later be possible through reference to a master copy of data that contains identifiers of study participants, aligned with the non-identifiable participant's code. As data manager, [name] will have responsibility for security of the identifiable data, and re-identifiable (coded) data.

► *Which investigator is responsible for de-identifying data?*

[name]

► *Are you using REDCap?*

Yes

Dissemination of program outcomes

It is important to disseminate research results to the healthcare community and research participants. This will be achieved through academic journal publication, conference, and internal institutional publication. A copy of the published articles related to the research will be sent to participants upon request. Articles will be either mailed by post or emailed as requested by participants.

References

